#### Step 3. Smoking Verification

Patients will complete a carbon monoxide (CO) breath test. A cut-off level of  $\geq 8$  ppm will be used to verify self-reported smoking.

#### Step 4. Obtain Informed Consent

Patients who express interest in participating will be informed in greater detail about the study and receive screening for eligibility criteria by the PI psychiatrist or the research assistant. The patients will learn about general requirements for participation (e.g., need for follow-up, participation in assessments, etc.) as well as risks associated with nicotine toxicity, nicotine withdrawal, blood sample and pharmacotherapy. If still interested and eligible, the patients will then be asked to provide written informed consent to participate, on a form approved by the Washington University School of Medicine Institutional Review Board. Study candidates will read the informed consent document and be given an opportunity to ask any questions regarding study participation. They will also complete the consent form. A follow up contact can be scheduled if potential participants would like to have more time to consider participation. Participants will receive a signed copy of the consent document.

### **2.d Randomization Method and Blinding**

The participants will be randomized with the ratio 1:1:1 to the treatment arm of combination NRT (nicotine patch and lozenge) plus smoking cessation counseling, or the treatment arm of varenicline plus smoking cessation counseling, or the treatment arm of placebo (patch and lozenge or pill) plus smoking cessation counseling.

Participants will be randomly assigned to 1) combination NRT plus counseling, 2) varenicline plus counseling, or 3) placebo plus counseling. SAS Version 9 statistical software will be used to generate the random assignment table stratified by CHRNA5 genotype rs16969968. The group assignment and genotype will be coded to ensure that the double blind is maintained, and the interface will prevent staff from having access to the participant's assignment and genotype until after the baseline and post treatment assessments have been completed.

### **2.e Risks and Benefits**

Risks associated with this research are judged to be minimal.

Smoking withdrawal is associated with a number of unpleasant symptoms such as sleep disturbance, hunger, craving, and negative mood. Most smokers have tried to quit in the past and are familiar with these phenomena.

With respect to the pharmacotherapy, participants will be made aware of the common side effects before they consent to participate in the study. It should be noted that the nicotine patch and lozenge are available over the counter. The nicotine patch has very few side effects, but participants may have a local skin reaction, and rarely, individuals may have a more systematic

---

allergic reaction. The most common side-effects associated with the nicotine patch are diarrhea, indigestion, nausea and vomiting, dry mouth, muscle and joint pain, sleeplessness, and abnormal dreams. Side effects associated with wearing an adhesive patch include skin rash, redness, and itching or irritation of the skin. The most likely side effects associated with the nicotine lozenge are heart burn, hiccup, nausea, upper respiratory track infection, coughing, and sore throat. In most cases, these side effects have been mild to moderate in intensity and go away once the patch is removed. Although most smokers have tolerance to nicotine, symptoms of acute nicotine toxicity (nausea and vomiting) are possible.

Varenicline is approved by the FDA for smoking cessation and is medically safe for most smokers except for individuals with severe (end stage) kidney failure or hypersensitivity to varenicline. In addition, although no causal relationship has been established, current labeling for varenicline (FDA, 2011) recommends monitoring for serious neuropsychiatric symptoms including changes in behavior, agitation, depressed mood, suicidal ideation, and suicidal behavior. Varenicline labeling also notes that some individuals with pre-existing psychiatric conditions may experience worsening of their conditions. Preliminary data from the University of Wisconsin Center for Tobacco Research and Intervention (UW-CTRI) smoking cessation trials showed comparable rates of discontinuation and adverse events due to NRT and varenicline. The low rate of serious adverse events is consistent with recent data on the safety of varenicline.

Blood draw may result in bruising, and very rarely, infection at the site of needle stick.

Some patients may experience emotional distress during evaluations for depression and anxiety.

Finally patient confidentiality would be compromised if unauthorized individuals were to establish the identity of any participant.

What is done to minimize the risks?

The principal investigator psychiatrist will be responsible for routine monitoring of unanticipated health events. This monitoring includes scheduled monthly meetings and review of written documentation. Unanticipated health event assessment, recording, reporting, and investigation will be accomplished through structured/standardized assessments of untoward occurrences/events, and regular monitoring by study physicians and other study investigators. The principal investigator has ultimate responsibility for ensuring that unanticipated health events are detected and reported in a timely manner. Health events that raise concerns (e.g., allergic reaction, symptoms suggestive of nicotine toxicity, significant change in mood, suicidal ideation) will be immediately reported to the study physician who will determine an appropriate course of action.

Potential side effects of combination NRT (patch and lozenge) will be closely monitored. The transdermal NRT is chosen for testing in participants for these safety reasons:

- 1) Transdermal NRT has slower absorption, lower peak serum level, and fewer cardiovascular effects, vs. varenicline, which has an FDA warning on use with cardiac patients
- 2) NRT is the most commonly used cessation medication in post-MI patients
- 3) Fewer drug interactions (vs. bupropion, which has an unsafe interaction with an MAO inhibitor if the patient is depressed).

---

Study participants will be closely monitored in accordance with current FDA recommendations as well as the consensus recommendations of the 2008 Guideline Panel which provides additional detailed instructions for clinicians regarding all FDA approved smoking cessation medications. We will follow the patient instruction and adverse events monitoring procedures used in the University of Wisconsin Center for Tobacco Research and Intervention (UW-CTRI). Patient education about possible side effects, access to a medication hotline, and ongoing monitoring will be consistent with FDA recommendations, clinical practice guidelines, and procedures successfully used in prior and ongoing UW-CTRI research using varenicline and combination NRT. This protocol is consistent with the 2010 FDA warning and recommendations for monitoring requirements regarding the black box warning of psychiatric risk for varenicline. In addition, we will make appropriate changes in study procedures if the FDA issues updates on varenicline.

All medical information and data from the interviews will be kept in a locked file cabinet in a locked office and identified by a code number. The master list of subject names will be kept in a separate locked file cabinet in a separate locked office by the Principal Investigator. Computerized research data are identified only by subject identification numbers and codes, and confidential data files are password protected. Written records of counseling sessions and audio recordings of sessions will be kept in a locked cabinet and will be destroyed within one year of the termination of the project. Audio recordings will be obtained if authorized by the participant. Only authorized individuals will be permitted to review these records. We have followed these procedures in the past without any breeches of confidentiality, and we feel certain that we will be able to maintain the same level of security for this project.

## BENEFITS

The potential benefits for smokers participating in this study include the chance to receive free smoking cessation counseling and pharmacotherapy, both of which double a smoker's odds of quitting.

In addition, this research has the potential to provide improved treatment strategies for clinicians trying to help patients quit smoking. This could result in more efficient provision of a maximally effective intervention for smokers.

The proposed research will test combination NRT and varenicline in patients with different genetic markers and identify effective pharmacotherapy according to the genetic markers. The results from this study will allow researchers to determine which smoker subgroups will benefit from pharmacotherapy and which smoker subgroups will not. This should contribute to the improvement of standard clinical care of such patients, and may result in improved medical outcomes. Given the limited risks of NRT and varenicline, and the limited adverse effects, we believe that the potential risks involved in participating in the study are outweighed by the benefits to both society and the individual.

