### **B2 Rationale for this Study**

Our overarching goal is to identify the most appropriate genetically informed smoking cessation treatments for smokers hoping to quit.

Our recent finding suggests that the effect of pharmacotherapy on cessation varies with genotype (nicotinic receptor gene, *CHRNA5*): pharmacotherapy significantly increases abstinence amongst individuals with the high-risk genetic variants, but provides little benefit to individuals with the low-risk variants. The genotype is useful to predict relapses and response to medication (Chen et al, 2012). Weighing both risk and efficacy on cessation success we will identify smokers who are more likely to relapse, and need pharmacotherapy in order to attain optimal outcomes versus those who will receive little benefit from pharmacotherapy. This work can lead to personalized treatment that promotes long term cessation success by focusing pharmacotherapy use on those who can benefit from it.

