## **C Study Objectives**

### **C1 Primary Aim**

Specific Aim 1: To recruit 822 participants who are active smokers in a smoking cessation trial. All patients will be randomized to combination NRT (Nicotine Replacement Therapy) with nicotine patch and lozenge, or varenicline, or placebo for 3 months. All patients will receive intensive smoking counseling. These patients will be assessed in person at baseline, 3 months (if biochemical verification of abstinence is needed), 6 months (if biochemical verification of abstinence is needed), and by telephone at the last day pre-quit, quit date, 1 week, 2 weeks, 4 weeks, 3 months (if biochemical verification of abstinence is not needed), 6 months (if biochemical verification of abstinence is not needed) and 1 year after the quit date.

Specific Aim 2: To determine if the effect of cessation pharmacotherapy (combination Nicotine Replacement Therapy (NRT) vs. varenicline vs. placebo for 3 months) on abstinence varies significantly with genotype. We will examine the association between two genetic variants in the CHRNA5 gene and treatment on smoking cessation success (abstinence at end of treatment (ABST\_EOT)). We will test the main effects of pharmacotherapy and genotype, as well as the interaction between them. Secondary cessation outcomes include abstinence at 6 months and 1 year.

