## D Study Design

### D1 Overview or Design Summary

This is a rs16969968 based stratified randomized controlled trial design examining the effects of one experimental factor (combination NRT vs. varenicline vs. placebo for 3 months) and one non-experimental participant characteristic: *CHRNA5* genotypes associated with high, intermediate, and low risk levels for nicotine dependence and cessation failure. Based on the frequency distribution of these genotypes, there will be sufficient numbers of each genetic groups represented in the active and placebo arm. We will examine the main effects of medication (cNRT vs placebo as well as varenicline vs. placebo) and genotypes (high, intermediate, and low risk), as well as the pharmacogenetic interaction between the genotypes and medication on the primary cessation outcome (abstinence at end of treatment, ABST\_EOT) and other outcomes (abstinence at 6 months and 1 year). We choose the primary efficacy measure of abstinence at 3 month (EOT) because our preliminary data from the UW-TTURC trial suggest the genetic effects on cessation take place in the early cessation stage. Our hypothesis is that NRT significantly increases smoking abstinence in patients possessing high-risk genotypes, but not amongst patients without such genotypes.

This experiment will achieve Aims 1 and 2 by answering the following questions:

- 1) Is there a genotype X Pharmacotherapy (cNRT vs. placebo) interaction with regard to abstinence?
- 2) Is there a genotype X Pharmacotherapy (varenicline vs. placebo) interaction with regard to abstinence?

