### ***F3 Analysis Plan***

All analyses will first be conducted separately for European Ancestry (EA) and African American (AA) due to distinctly different allele frequencies and linkage disequilibrium across ancestry. If consistent genetic effects are seen across ancestry, samples of EA and AA ancestry will be combined in analyses with the covariate of race.

---

We will compare the abstinence outcome in the two placebo groups (placebo nicotine patch plus placebo nicotine lozenge vs. placebo varenicline pill). If they are comparable which is consistent with prior experience of other placebo-controlled smoking cessation trials, they will be pooled for further analyses.

The primary outcome is CO-confirmed point prevalent abstinence at end of treatment (12 weeks), defined if subjects deny smoking during 7 days prior of the end of treatment and provide a breath sample with CO <8 ppm.

Hypothesis #1 is to examine whether medication effect (cNRT vs. placebo) varies with CHRNA5 (i.e. a genotype X medication interaction). A series of generalized linear models will be used to examine main effects of genotype (rs16969968) and medication before testing genotype x medication interactions, with sex, age, and study cohort as covariates using logistic regression models.

Hypothesis #2 is to examine whether medication effect (varenicline vs. placebo) varies with CHRNA5 (i.e. a genotype X medication interaction). A series of generalized regression models will be used to examine main effects of genotype (rs16969968) and medication before testing genotype x medication interactions, with sex, age, and study cohort as covariates using logistic regression models.

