#### Analysis Plan.

We will use generalized linear models with logit as the link function to model the primary outcome (7-day point prevalence abstinence at 12 weeks/end of treatment). We will construct contrast models for each specific hypothesis testing and compare the goodness of fit for each contract. The primary method of analysis will be estimating a standard series of regression equations to test main effects, and gene – environment interaction (effect moderation).

Our primary analyses will focus on SNPs, rs16969968, tagging nicotinic receptor genes *CHRNA5-A3-B4* and medication in our hypotheses testing for gene-medication interactions. Additional covariates include age, gender, measures of nicotine dependence severity (such as pre-quit cigarettes smoked per day), adherence, and non-genetic factors.

Secondary cessation outcomes include CO-confirmed 3-month continuous abstinence with a 1-week grace period, 7-day abstinence at 6 months, and 1 year, time to relapse (using Cox regression models), and withdrawal severity. Generalized Estimation Equation (GEE) will be used in longitudinal models comprising abstinence outcomes across 3 months, 6 months, and 1 year in secondary analyses.

Detailed analysis plan is included in the Statistical Analysis Plan (SAP) in Appendix K10.

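### The planned genotype-by-medication interaction can show that drug effects differ between genotypes, but no specified analysis supports the claim that some genotype groups do not benefit

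*Combined protocol and SAP*

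**What the plan says.** The aim appears in three places. The BENEFITS text under 2.e says the results will allow researchers to "determine which smoker subgroups will benefit from pharmacotherapy and which smoker subgroups will not". D1 hypothesises that "NRT significantly increases smoking abstinence in patients possessing high-risk genotypes, but not amongst patients without such genotypes", and A1 says the same of haplotypes. B2 gives the purpose as directing medication to those who can gain from it: "Weighing both risk and efficacy on cessation success we will identify smokers who are more likely to relapse". It contrasts these smokers with others expected to gain little.

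The formal hypotheses are narrower. F3 states: "Hypothesis #1 is to examine whether medication effect (cNRT vs. placebo) varies with CHRNA5 (i.e. a genotype X medication interaction"). Hypothesis #2 is the same for varenicline, and A2 repeats both. On the model, the Analysis Plan under F3 says: "We will use generalized linear models with logit as the link function to model the primary outcome". The primary method is "estimating a standard series of regression equations to test main effects, and gene – environment interaction (effect moderation"). F1 gives power for the interaction only: 0.84 for an interaction effect size of 2.0, with two-sided alpha 0.05 and 20% abstinence on placebo.

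Other analyses are also stated. C1 says: "We will test the main effects of pharmacotherapy and genotype, as well as the interaction between them". F3 and F4 add: "We will construct contrast models for each specific hypothesis testing and compare the goodness of fit for each contract", and the content of those contrasts is not given. F4 lists chi-square, logistic and Cox models, and F3 lists GEE for longitudinal outcomes. F3 and F4 refer to Appendix K10 for the detailed SAP. In the supplied text K10 is a heading with nothing under it.

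**The concern.** The stated aim has two halves: some genotype groups benefit, and others do not. The interaction test bears on whether the effects differ. It does not address the second half, because two groups can differ clearly while both benefit.

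The A1 and D1 hypothesis is phrased as significant in one group but not in the other. That invites a reader to take a non-significant result in the smaller or lower-risk group as evidence of no benefit. With no genotype-specific interval planned in the supplied text, nothing would show how large a benefit the data still allow. B2 would use the findings to decide where medication is focused, so a no-benefit conclusion unsupported by the data would matter.

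**Working it through.** **Inputs from the documents.** N = 822 randomised 1:1:1 (F1, 2.d), so 822/3 = 274 per arm. Placebo abstinence is 20%, two-sided alpha 0.05, interaction effect size 2.0, read as an odds ratio (F1). The 274 on placebo assumes that the two placebo halves are pooled, which F3 makes conditional on their being comparable.

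**Assumptions.** The documents give no genotype frequencies and no placebo rates by genotype. I take a genotype group as 30% to 88% of an arm; the top of the range stands for pooling everyone who is not high-risk.

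**Step 1: the plan's own figure.** The power of 0.84 concerns the interaction, not absence of benefit. It cannot be reproduced uniquely because genotype frequency and coding are not stated. It bears on this point only in showing what the trial was sized for.

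**Step 2: what a zero difference would leave open.** The 95% half-width for a difference between two equal groups with abstinence p in both is 1.96 × √(2p(1−p)/n). For n = 82 and p = 0.20: 1.96 × √(0.32/82) = 0.122.

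| Share of arm | n per arm | Half-width, p = 20% | Half-width, p = 30% |
|---|---|---|---|
| 30% | 82 | 12.2 points | 14.0 points |
| 42% | 115 | 10.3 | 11.8 |
| 60% | 164 | 8.7 | 9.9 |
| 88% | 241 | 7.1 | 8.2 |

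The 30% column is included because the protocol expects smokers without the high-risk variants to quit more often unaided. F3 analyses each ancestry group separately first, which makes these groups smaller and the intervals wider.

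**Step 3: how often a working drug would look non-significant in one group.** BENEFITS says medication doubles the odds of quitting. From 20%, the odds go from 0.25 to 0.50, so abstinence becomes 33.3%, a gain of 13.3 points. Power for that comparison is Φ[(Δ − 1.96√(2p̄(1−p̄)/n)) / √((p₁(1−p₁)+p₂(1−p₂))/n)]. For n = 96: (0.1333 − 0.1251)/0.0631 = 0.13, so power is 0.55.

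| Share of arm | n per arm | Power |
|---|---|---|
| 20% | 55 | 0.35 |
| 35% | 96 | 0.55 |
| 50% | 137 | 0.71 |
| 65% | 178 | 0.81 |

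A non-significant result would thus occur 19% to 65% of the time with the drug working as the protocol says it does.

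**Step 4: a true interaction of 2.0 with benefit in both groups** (assumed placebo rates).
- Low-risk, placebo 30%, OR 1.5: odds 0.4286 × 1.5 = 0.6429, abstinence 39.1%, gain 9.1 points (about 1/0.091 = 11 treated per extra abstainer).
- High-risk, placebo 10%, OR 3.0: odds 0.1111 × 3.0 = 0.3333, abstinence 25.0%, gain 15.0 points.

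The interaction odds ratio is 3.0/1.5 = 2.0, the planned size, yet the low-risk group gains.

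**Step 5: size needed to show no benefit.** With a true difference of 0, p = 20%, one-sided 0.025 and 80% power, n = (1.96 + 0.8416)² × 2 × 0.16/margin². A 10-point margin gives 7.849 × 0.32/0.01 = 251.2, so 252 per arm within the genotype group. A 5-point margin gives 1,005. These margins are illustrations. A whole arm has 274.

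**The case against.** The operative hypotheses and the questions in A1, A3 and D1 ask only whether the effect varies with genotype, and a formal interaction test is the right tool for that. The BENEFITS sentence is a risk-benefit justification, not an objective. The contrast models are unspecified and could include genotype-specific drug effects, and K10 might contain the intervals. All of this is fair. It limits the point to the supplied text, and it means that the gap lies between the claims and the specified analysis, not in the choice of test. It does not remove the gap: A1, D1 and BENEFITS still promise more than an interaction can deliver, whatever K10 contains.

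Three stronger readings are tempting and are not supported.
- **That the interaction is the only planned test.** Main-effect, contrast, chi-square, Cox and GEE analyses are also stated. None is specified to show absence of benefit within a genotype.
- **That the plan has a rule treating non-significance as no benefit.** No section sets one. The D1 wording invites that reading and concerns NRT only.
- **That the odds scale is likely to reverse the order of absolute benefit.** At an interaction of 2.0, reversal needs widely separated placebo rates, such as 35% with OR 1.5 (gain 9.7 points) against 5% with OR 3.0 (gain 8.6). At 30% against 10% the order is kept (step 4). If one group truly has no effect, an odds ratio of 1 and a difference of 0 coincide. With no interaction the absolute gains do differ (OR 2.0 in both groups: 16.2 points from 30%, 8.2 from 10%), which is a reason to report differences, not evidence that the test misleads.

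**Conclusion.** The concern stands in this form: the plan aims to say which genotype groups do not benefit, and no specified analysis in the supplied text supports that statement. At 20% abstinence in both arms, a zero difference would leave gains of about 7 to 12 points unexcluded for groups of 88% to 30% of an arm; at 30% abstinence, about 8 to 14 points. The planned interaction is compatible with a 9-point low-risk gain.

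These sizes rest on assumed genotype shares, assumed genotype-specific placebo rates, pooled placebo halves and a simple unadjusted comparison within each group. Covariate adjustment, or a per-allele model that borrows across groups, would change the widths somewhat but not the logic. The content of K10 is unknown and could supply the missing intervals. This should be changed, but it does not invalidate the interaction test.

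**What to change.** In F3, for each genotype group and each drug, report the standardised abstinence difference versus placebo with its 95% confidence interval, from the same logistic model and beside the interaction odds ratio. State how genotype is coded in that model. Add that any statement about who does not benefit will rest on those intervals and not on a non-significant subgroup result; otherwise the conclusion is limited to whether effects differ by genotype. If K10 already contains this, a cross-reference in F3 is enough.

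Reword the hypothesis in A1 and D1 to a larger effect in high-risk than in other genotypes, and soften the BENEFITS sentence and the matching B2 rationale accordingly.

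A no-benefit margin is optional. If one is wanted, it must be fixed before unblinding, and the protocol should say that it is unlikely to be met at this size (step 5).

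The cost is protocol and SAP wording plus standard post-estimation output, with no new data and no change to trial conduct. The downside is a more modest stated claim.
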